Recent advances in continuous glucose monitoring (CGM) technology including greater accuracy, longer wear time, and no need for calibration, have led to an increase in use.¹² Randomized controlled trials of modern devices demonstrate improvement in A1c, time target range, hypoglycemia and patient reported outcomes in persons with type 2 diabetes (T2D).^{13,14,15} Moreover, real-world evidence demonstrates a reduction in A1c, diabetes distress, and hypoglycemia, and high ease of use.¹⁶ Other real world evidence found an association between near-continuous CGM and reduced hospitalizations and acute diabetes complications.^{17,18} Among older adults, treatment satisfaction and use was high, and associated with improvement in glucose control.^{19,20} However CGM is underutilized for most patients with T2D due to a variety of factors, including costs and coverage issues, time constraints imposed by implementation and use, and complexity of obtaining and interpreting data.^{12,21} In addition, there limited studies addressing optimal strategies for implementation in busy clinics. In this study we evaluate a remote CGM program utilizing Dexcom G6 CGM for recently hospitalized patients with T2D.

Aim 1: Determine the efficacy of CGM following hospital discharge among patients with T2D. We will record change in glucose metrics from discharge to 12 weeks follow-up, including % time in range 70-180 mg/dl (TIR), % time below 70 mg/dl, 54 mg/dl, and above 180 mg/dl (TAR), severe (level 3) hypoglycemic events, mean glucose, coefficient of variation, and A1c. **We will assess the primary objective by testing the relationship between CGM use (including prior inpatient use) and either change in glucose metrics or individualized % of TIR.**

Aim 2: Evaluate the utility of CGM use and impact of remote monitoring dashboard among recently hospitalized patients with T2D. A dashboard will identify patients not meeting personalized % TIR, triggering customized reports and decision support to be communicated to the patient and the usual diabetes provider. We will assess the proportion of patients with successfully transmitted data as well as change in insulin dose. A survey to the usual diabetes provider will assess usability of reports and decision support.

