Aim 3: Evaluate patient reported outcomes among patients with T2D using CGM following hospital discharge. Outcomes will include treatment satisfaction (Diabetes Treatment Satisfaction Questionnaire, Benefits of CGM/Burdens of CGM), self-management and psychosocial measures (Diabetes Distress Scale). We will assess whether % CGM wear time, prior inpatient use of CGM, or change in glucose metrics are associated with patient reported outcomes.

Exploratory Aim 1: Assess whether CGM wear time or glucose control is associated with readmission and outpatient visits.

Exploratory Aim 2: Assess whether participants maintain use of CGM and glucose metrics up to 6 months of use following discharge.

SIGNIFICANCE

Diabetes is present in at least 25% of hospitalized patients and is associated with increased costs and hospital readmission.²² While diabetes is not usually the primary reason for admission, the hospital setting offers an opportunity to identify vulnerable populations and implement interventions to improve diabetes care after discharge. In fact, despite the availability of a growing number of diabetes therapies and technologies, the proportion of patients achieving personalized A1c targets has not changed in the past decade.²³ Moreover, there are considerable disparities across demographic and socioeconomic groups.^{23,24}

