Outpatient care has shifted toward population based or value based care models, in which patients at highest risk receive greater intensity of care.³⁵ High risk patients include those who have been recently hospitalized or who have an elevated A1c, and both criteria align with incentives for reimbursement. Most electronic medical records (EMR)s provide a dashboard for tracking A1c. However, A1c is often not actionable for a variety of reasons, including recent changes in therapy that are not reflected by A1c, and conditions such as anemia that affect the accuracy of A1c measurement.⁹ In insulin-requiring patients, A1c as a measure of mean glucose does not reflect the within day or between day variations in glucose levels. Thus, self-monitored blood glucose (SMBG) data are needed to inform adjustments in therapy. Unfortunately SMBG is often not performed at an optimal frequency to be able to appreciate glucose patterns,³⁶ SMBG cannot warn patients of actual or impending hyperglycemia or hypoglycemia,^{37,38} and there is not an efficient method for communicating data to healthcare providers.³⁹ Therefore additional strategies are needed to optimize population health approaches while at the same time emphasizing a patient centered approach.⁴⁰

INNOVATION

Unlike A1c or even SMBG, continuous glucose monitoring (CGM) facilitates the identification of daily glucose patterns which can directly inform treatment decisions or lifestyle changes. CGM also improves the recognition of hyperglycemia and hypoglycemia. However, CGM is not widely available, even in patients who qualify based upon professional society guidelines,^{41,42,43} in part due to stringent criteria set forth by payers, but also due to the need to be attached to a device, skin allergies, difficulty with adhesion, concerns about accuracy and need for patient training.⁴⁴ Moreover the sheer amount of data to be processed can be overwhelming for patients and prescribers, and there are challenges posed by the amount of time and effort required to transmit and interpret CGM data.⁴⁵

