Study Extension: Patients will transition to standard of care observational extension phase of the study in order to ascertain whether patients continue use of CGM through their usual care provider. General instructions will be provided to the patient and provider based upon the patient's payer (including use of durable medical equipment company or pharmacy). We will assess device use, glucose metrics, medication adjustments, healthcare utilization, and A1c.

Provider survey: At 12 weeks, Clinicians will be contacted via email to participate in a web-based survey. Participants provided electronic informed consent prior to taking the survey. The survey is anticipated to take approximately 15 minutes. An incentive in the form of a \$20.00 Amazon gift card will be electronically distributed to providers who complete the survey. Survey elements will include:

- Practice characteristics: provider type, years in practice, practice setting, specialty, characteristics (percentage of patients with diabetes, familiarity of CGM use [5-point scale], frequency of interpreting CGM reports).
- Utility of CGM reports to make adjustments to therapy. There is no validated survey specifically assessing utility of CGM reports for clinicians. The Sustainability Use Survey (SUS), a 10-item questionnaire, is widely used for measuring perceived usability of a system.⁵⁵ The SUS-2 is the best combination of SUS items that predict an SUS score with high accuracy; therefore, the 2 items were included in the provider survey in lieu of using the full SUS to enable benchmarking of usability and minimize provider burden. The 2 items used in the CAS are: 1) *I thought the CGM report was easy to use*, and 2), *I found the CGM report was cumbersome to use*. These questions map to SUS 03 and SUS 08, respectively, and when analyzed together are known as the SUS-2. The questions are analyzed based upon a 5-point Likert scale. Benchmarking SUS scores: SUS-2 scores and individual item scores have been compared against a large dataset of ~500 published studies of SUS data. The average raw SUS score (at the 50th percentile) is 68.
- Additional questions will include (5-point likert scale)
 - *I found the Ambulatory Glucose Profile to be helpful for assessing glucose control*
 - *I found the Ambulatory Glucose Profile to be helpful for making adjustments to therapy*
 - *I found the report recommendations to be helpful for making adjustments to therapy*

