The database used for this study is REDCap, which is a secure web-based application for building and managing data. It is designed specifically for clinical research and administered by the OSU Center for Clinical and Translational Research. Permission for data access or entry will be granted or revoked at a level that is appropriate for each individual involved in the study. Following verification, data will be locked. Data and data labels can be downloaded selectively (for interim progress reports) or in entirety (end of study) directly from REDCap in SAS or Excel format.

Baseline Data:

- Demographics: gender, race/ethnicity, age, marital status, education, employment, insurance, marital status, contact information
- History: diabetes duration, tobacco use, microvascular/macrovascular complications, heart failure, conditions requiring anticoagulation (thromboembolism, atrial fibrillation), hypertension, hyperlipidemia, liver disease, hypoglycemia awareness, reason for hospital admission
- Medications: pre-admission, discharge, and follow-up insulin use and total daily dose, insulin type, other glucose-lowering medications, steroid use, anticoagulants, antiplatelets
- Exam: weight, height, BMI
- Surveys: MPSSS, eHEALS, SNS-3
- Labwork: eGFR, A1c, glucose level on admission and discharge
- Patient reported outcomes: DTSQs, DDS
- Additional patient questions about CGM use
- CGM target (Table 4)

Visit 1, 2, 3:

- Glucose data: detailed below
- Communication: to usual care provider (summary only, summary with advice)
- Diabetes medications, bolus insulin use, basal insulin dose, missed doses
- Adverse events (sensor irritation, infection, bleeding)
- Additional patient questions about CGM use
- Healthcare Utilization: PCP visit, education visit, endocrinology visit, hospital readmission, emergency visit
- CGM target (Table 4)

Visit 4:

- Glucose data: detailed below
- Communication: to usual care provider (summary only, summary with advice)
- Diabetes medications: non-insulin medication use by class, bolus insulin use, basal insulin dose, missed doses
- Adverse events (sensor irritation, infection, bleeding)
- Healthcare Utilization: PCP visit, education visit, endocrinology visit, hospital readmission, emergency visit
- Patient reported outcomes: DTSQs, DTSQc, DDS, BenCGM, BurCGM
- Additional patient questions about CGM use
- A1c
- CGM target (Table 4)

Visit 5, 6

- Glucose data: detailed below

Visit 7

- Glucose data: detailed below

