- Usual Care Provider usability: SUS-2 (ease of use, cumbersome to use), CGM report helpful in assessing glucose control, ambulatory glucose profile helpful for making adjustment in therapy, report recommendations helpful for making adjustments to therapy, whether Clarity website was accessed.
- % of usual care providers reporting review of data

Aim 3:

Primary:

- Change in DTSQ scores from baseline to 12 weeks

Secondary:

- Change in DDS from baseline to 12 weeks
- Patient reported outcomes (DTSQ, DDS, BenCGM, BurCGM).

Endpoints for Exploratory Aim 1:

- healthcare utilization (clinic visits, education visit, hospital readmission, emergency visit)

Endpoints for Exploratory Aim 2 (Extension Phase): *By 18 months (the end of the last 90 day visit), we anticipate that a subset of patients (75%) will have at least 12 additional weeks of data following the primary endpoint at 12 weeks. We will assess the following metrics among users and compare to nonusers:*

- Change in % CGM wear from 12 weeks to 24 weeks
- Change in glucose metrics from 12 weeks to 24 weeks.
- Change in insulin dose from 12 weeks to 24 weeks.
- Patient reported barriers to continued CGM use (5-point Likert from not important at all to very important, unless otherwise noted):
 - Cost/coverage concerns (if important or very important, then answer the following)

- Insurance did not cover CGM (yes/no)
- Insurance partially covered CGM but co-pay was too high (yes/no)
- Usual care provider would not prescribe CGM (yes/no)
- Too much hassle to order/obtain CGM
- Too many alarms
- Having device attached to the body/lack of privacy
- Do not understand what to do with the information
- Unreliable/does not work
- Discomfort/pain
- Too time-consuming
- Interferes with sleep
- Healthcare utilization (PCP visit, education visit, endocrinology visit, hospital readmission, emergency visit)

Sample Size

We anticipate enrollment of 120 patients over a 1 year period with 20% drop-out. The following data support this sample size.

Aim 1:

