- DTSQ: In the LANDMARK study, 94% of participants with T2D were satisfied or very satisfied (Question 1 of the DTSQ). In a randomized study of 101 patients with T2D using the Freestyle Libre Flash glucose monitor (an intermittently scanned glucose monitoring device), mean (SD) DTSQc score per subject for each question was 2.47 (0.77) with CGM vs. 2.18 (0.83) in the control group ($P = 0.053$). Thus, we would anticipate a change in DTSQc that is proportional.¹³
- DDS: In the LANDMARK study, the DDS decreased from 2.67 (SD 0.65) to 1.85 (0.65) from baseline to 12 weeks. We would anticipate a similar change in DDS score.
- BenCGM, BurCGM: In a large study of patients with type 1 diabetes, there was a significant difference in BenCGM (4.48 vs. 4.19, $p<0.001$) and BurCGM (1.69 vs. 2.35, $p<0.001$) among CGM users vs. non-

users, respectively. Thus, we anticipate that both scores will be associated with CGM wear time in the present study.

Analysis

Descriptive statistics will summarize the sample characteristics and distribution of each variable. Data will be screened for normality, outliers, and homogeneity. Continuous variables with normal distribution will be reported as mean (standard deviation) while non-normal distribution will be reported as median (interquartile range). Binary variables will be reported as number (percentage). Change over time in continuous variables will be reported as paired t-test or nonparametric test as appropriate. Difference of proportions between groups for binary variables is tested by Fisher's test (two groups) or chi-square test (three or more groups). Statistical significance will be determined at p-value of <0.05.

For Aim 1, linear regression can be used for checking the relationship between %CGM wear time and change in glucose metrics. Appropriate transformation may be needed if the residual plots show obvious violation of linear regression assumptions. Logistic regression can be used for checking the association between % CGM wear time and % meeting individualized TIR or change in % of patients who meet their individualized TIR. For choosing the predictors of change in TIR from baseline to 12 weeks, we can first include a subset of the exploratory variables depending on the descriptive statistics and clinical context. If necessary, further variable selection (stepwise selection) can be conducted to make the analysis reliable. In addition, we will assess baseline predictors of glucose metrics.

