Participants may benefit from more intensive interaction with study staff, through improved glycemic control as well as close follow-up and anticipatory guidance. Benefits to society include improved glycemic control and hospital readmission, which may result in reduced medical costs, particularly among uninsured individuals. The risks are primarily related to breach of confidentiality and are limited, though still possible. Expert guidelines recommend glucose monitoring among insulin requiring patients using periodic finger stick glucose measurements or via continuous or semi-continuous interstitial measures (intermittently scanned glucose monitoring or CGM). CGM greatly reduces the need for fingerstick glucose monitoring and therefore minimizes discomfort related to glucose monitoring as it only needs to be replaced every 10 days. However, CGM is not widely adopted, primarily due to the expense. Moreover, CGM users have easy access to glucose values at any time and therefore are more likely to use the data to modify behaviors that affect glucose control. Thus patients may benefit from this technology as a result of participating in the study. Given the safeguards that are put in place, the potential benefits should outweigh the risks.

Usual Care Providers: Providers may obtain indirect benefit from additional support provided by the study in training patients to use CGM, assisting with obtaining and interpretation of reports, and improved glucose control among their patients.

Importance of the Knowledge to be Gained

The importance of the knowledge is in the understanding of the role of diabetes, in particular glucose control, on patient satisfaction outcomes in patients with cancer who were recently discharged from hospital. Currently, few studies have examined glucose control in this population following inpatient hospitalization. The rising epidemic of diabetes will continue to contribute significantly to the morbidity of these patients, frequently necessitating hospital care. Providing solutions to this problem is of considerable urgency. Therefore, the potential benefits outweigh the given the aforementioned risks.

REFERENCES

¹ American Diabetes Association. Economic Costs of Diabetes in the U.S. in 2017. *Diabetes Care*. 2018 May;41(5):917-928. doi: 10.2337/dc18-0007.

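### The extension-phase comparison of CGM users with nonusers has no specified adjustment, although continued use depends partly on payer and on other selection factors

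*Combined protocol and SAP*

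**What the plan says.** The aim, under Specific Aims, is to "Assess whether participants maintain use of CGM and glucose metrics up to 6 months of use following discharge". The endpoint list for Exploratory Aim 2 adds a comparison: "We will assess the following metrics among users and compare to nonusers". The listed metrics include glucose metrics, insulin dose and healthcare utilization.

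The Study Extension section says that after week 12 patients obtain CGM through their usual care provider. It continues: "General instructions will be provided to the patient and provider based upon" the patient's payer. Cost and coverage is the first barrier on the Exploratory Aim 2 list, with follow-up questions on whether insurance refused cover or the co-pay was too high. The benefits section states: "However, CGM is not widely adopted, primarily due to the expense".

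Other sections give a wider set of reasons. Innovation says CGM is not widely available "in part due to stringent criteria set forth by payers, but also due to the need to be attached to a device", and goes on to skin, adhesion, accuracy and training. Specific Aims says CGM is underused "due to a variety of factors, including costs and coverage issues, time constraints imposed by implementation and use". The barrier list also has items on hassle, alarms, wearing a device, understanding, reliability, pain, time and sleep.

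Baseline Data, under Data Collection and Management, includes "gender, race/ethnicity, age, marital status, education, employment, insurance, marital status, contact information". In Analysis, the between-group sentence reads "Difference of proportions between groups for binary variables is tested by" Fisher's test or chi-square. The regression and variable-selection text is written for Aims 1 and 3.

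**The concern.** Nobody is assigned to continue or stop CGM after week 12. A patient's payer can affect whether sensors are obtained, and may also affect clinic access, medication and emergency visits. If so, a raw difference between users and nonusers mixes any association with CGM with differences between payers. The investigators already treat insurance as a covariate for a related outcome: their readmission analysis in Preliminary Data adjusted for it, and readmission is one of the utilization outcomes compared here.

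The publication plan assigns the extension data to a manuscript. A raw difference in A1c, dose or utilization could be published there with nothing in the plan committing the analyst to adjust for payer, week-12 control or week-12 wear, all of which are collected.

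**Working it through.** The extension contrast has no sample-size or power statement, so there is no plan figure to reproduce. The calculation below shows scale only.

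**Inputs from the documents**
- Payer mix in the earlier discharge study (Table 1, N=158): none 11, private 52, Medicare 35, Medicaid 60.
- Extension sample: 75% of patients are expected to have the extra 12 weeks of data, but the base is not stated. Of 120 enrolled this is 90. Of the 96 left after 20% dropout it is 72.
- SD of A1c change: 0.9 points (Sample Size, Aim 1).

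**Assumptions, not in the documents**
- Continuation rates by payer, in the table below.
- Medicaid or uninsured patients drift 0.3 to 0.5 A1c points worse from week 12 to 24 for reasons unrelated to CGM.
- The groups are compared with an unadjusted two-sided t-test at 5%. The plan names no between-group test for continuous variables.

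**Formulas**
- Share of Medicaid or uninsured among users = (their continuers) / (all continuers), and likewise among nonusers.
- Spurious difference = payer gap × (share among nonusers − share among users).
- SE = 0.9 × √(1/n_users + 1/n_nonusers). The false-positive rate comes from the noncentral t distribution with noncentrality equal to spurious difference / SE.

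**Central case, continuation 10/80/70/40% (none/private/Medicare/Medicaid)**
- Continuers: 1.1 + 41.6 + 24.5 + 24.0 = 91.2 of 158, or 57.7%.
- Medicaid or uninsured among users: 25.1/91.2 = 27.5%. Among nonusers: (71 − 25.1)/(158 − 91.2) = 45.9/66.8 = 68.7%. Gap: 41.2 points.
- Spurious difference: 0.412 × 0.3 = 0.12 to 0.412 × 0.5 = 0.21 A1c points.
- SE: 0.215 at n=72 and 0.192 at n=90. Noncentrality runs from 0.124/0.215 = 0.58 to 0.206/0.192 = 1.07, which gives an error rate of 9% to 19%.

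| Continuation (none/private/Medicare/Medicaid) | Medicaid or none, users | Medicaid or none, nonusers | Spurious A1c difference | False-positive rate |
|---|---|---|---|---|
| 30/70/65/50% | 36.0% | 57.5% | 0.06–0.11 | 6–9% |
| 10/80/70/40% | 27.5% | 68.7% | 0.12–0.21 | 9–19% |
| 10/85/80/30% | 20.9% | 77.8% | 0.17–0.28 | 12–31% |

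**Sensitivity to the payer grouping.** If only having any insurance matters (147 of 158 insured), uptake of 70% against 30% gives users 96.9% and nonusers 85.1% insured, a gap of 11.8 points. The spurious difference is then 0.04 to 0.06 points. With an even split, a bias of 0.06 raises the error rate only to about 6%. The answer therefore depends on which payer classes differ and on how steep uptake is across them.

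**The case against.** The strongest case on the other side has several parts, and much of it stands.

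- **Silence is not a stated choice.** A reader might infer that the plan has chosen an unadjusted analysis. It has not. The Fisher and chi-square sentence is a general rule for binary variables and is not tied to the extension. The accurate statement is that no adjustment is specified.
- **Payer is one factor among several.** A reader might infer from the expense remark that the contrast is mainly between better- and worse-insured patients. That remark concerns CGM adoption in general. Other sections list many non-cost reasons, and no uptake by payer is given. The week-8 pre-filled certificate of medical necessity and the payer-specific instructions may also weaken sorting by payer.
- **The size rests on stacked assumptions.** Both the continuation rates and the payer gap are invented, and weak sorting leaves the error rate near nominal. With 72 to 90 patients split evenly, the difference detectable with 80% power is 2.80 × 0.212 = 0.59 to 2.80 × 0.190 = 0.53 A1c points, so the largest spurious difference above is about half of that.
- **Coverage is measured.** Insurance is recorded at baseline and coverage barriers are asked at the end of the extension. The gap is in the analysis text, not in the data. The Human Subjects baseline list omits insurance, but that is editorial.
- **No causal claim is made.** The design is called observational and the aim is exploratory.
- **Adjusting for payer alone is not enough.** Engagement, week-12 control and provider willingness would remain.

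What survives is that the covariate text does not reach this contrast. The general commitment to assess baseline predictors of glucose metrics is not written for the extension either.

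**Conclusion.** The point holds in limited form. The plan commits to comparing self-selected users with nonusers, links continued access to payer, and specifies no adjustment. The contrast is plausibly confounded by payer along with the other selection factors the protocol lists.

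The size is unknown. The range of roughly 6% to 31% in place of 5% holds only under the assumed continuation rates, the assumed 0.3 to 0.5 point A1c gap, the Table 1 payer mix, an SD of 0.9 and 72 to 90 patients. The documents do not support saying that payer dominates the contrast. They also give no ground for extending the concern to the 12-week primary endpoints, which do not use this comparison.

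**What to change.** In the Exploratory Aim 2 endpoint list and in Analysis:

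1. State how a user and a nonuser are defined.
2. Compare the groups on A1c and insulin dose by linear regression, and on healthcare utilization by logistic regression (any event) or Poisson regression (counts).
3. Adjust each model for baseline payer class and for the week-12 value of the outcome, or for week-12 A1c and wear time. All are already collected. Fix the payer grouping in advance; Medicaid or none against private or Medicare is one option and uses one degree of freedom.
4. Report the result as an exploratory association, and show the coverage-barrier answers beside it so that readers can see how much nonuse patients attribute to coverage.

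The cost is a few sentences, a few degrees of freedom and a slightly wider interval. No new data are needed. Adjustment reduces measured confounding only. Selection by engagement, device burden or provider willingness may remain, which is why the wording in step 4 matters.
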